6 SELECTION AND WITHDRAWAL OF SUBJECTS

The nonconsecutive numbering and application of letters to some numbers in this section reflect changes that have occurred with protocol amendments.

6.1 Inclusion criteria

To be eligible to participate in this study, all of the following criteria must be met as specified.

6.1.1 Inclusion criteria for all subjects

1. An Institutional Review Board (IRB)/Independent Ethics Committee (IEC) approved written Informed Consent form is signed and dated by the parent(s) or legal representative(s). The Consent form or a specific Assent form, where required, will be signed and dated by minors.
- 2a. Subject/legal representative is considered reliable and capable of adhering to the protocol (eg, able to understand and complete diaries), visit schedule, or medication intake (including BRV oral solution or tablets) according to the judgment of the Investigator.
14. For female subjects, the subject is
 - Not of childbearing potential

-OR-

- Of childbearing potential, and
 - Is not sexually active
 - Has a negative pregnancy test

-OR-

- Of childbearing potential, and
 - Is sexually active
 - Has a negative pregnancy test
 - Understands the consequences and potential risks of inadequately protected sexual activity, understands and properly uses contraceptive methods, and is willing to inform the Investigator of any contraception changes. Medically acceptable contraceptive methods for the study include, but are not limited to:
 - Oral or depot contraceptive treatment with at least ethinylestradiol 30µg per intake or ethinylestradiol 50µg per intake if also taking one of the following: carbamazepine, phenobarbital, primidone, phenytoin, oxcarbazepine, St. John's Wort, or rifampicin
 - Barrier contraception: intrauterine device, diaphragm with spermicide, male or female condom with spermicide

6.1.2 Inclusion criteria for LTFU subjects only

3a. Male or female subjects having participated in a core study with a confirmed diagnosis of epilepsy and for whom a reasonable benefit from long-term administration of BRV is expected.

6.1.3 Inclusion criteria for directly enrolled subjects only

8. Subject is a male or female ≥ 4 years to <17 years of age.
9. Subject has a clinical diagnosis of POS according to the ILAE classification.
10. Subject has an EEG compatible with the clinical diagnosis of POS.
11. Subject has been observed to have uncontrolled POS after an adequate course of treatment (in the opinion of the Investigator) with at least 1 AED (concurrently or sequentially).
12. Subject had at least 1 seizure (POS) during the 3 weeks before the ScrV.
13. Subject is taking at least 1 AED. All AEDs need to be at a stable dose for at least 7 days before the ScrV. Vagal nerve stimulator-stable for at least 2 weeks before the ScrV is allowed and will be counted as a concomitant AED. Benzodiazepines taken more than once a week (for any indication) will be considered as a concomitant AED.

6.2 Exclusion criteria

Subjects are not permitted to enroll in the study if any of the following criteria are met as specified. Criteria that were in place before Protocol Amendment 3 have retained the previous numbering.

6.2.1 Exclusion criteria for all subjects

1. Subject is a pregnant or nursing female.
3. Subject has severe medical, neurological, or psychiatric disorders or laboratory values, which may have an impact on the safety of the subject.
5. Subject has planned participation in any clinical study of another investigational drug or device.
6. Subject has any medical condition, which in the Investigator's opinion, warrants exclusion.
29. Subject has $>1.5 \times$ upper limit of normal (ULN) of any of the following: alanine aminotransferase (ALT), aspartate aminotransferase (AST), alkaline phosphatase (ALP), or $>1.0 \times$ ULN total bilirubin ($\geq 1.5 \times$ ULN total bilirubin if known Gilbert's syndrome). If subject has elevations only in total bilirubin that are $>ULN$ and $<1.5 \times$ ULN, fractionate bilirubin to identify possible undiagnosed Gilbert's syndrome (ie, direct bilirubin $<35\%$).

N01349 subjects with a total bilirubin $>$ ULN may be considered for the study if benign unconjugated hyperbilirubinemia is suspected in the context of prolonged neonatal jaundice, after discussion with the medical monitor.

For randomized subjects with a baseline result $>$ ULN for ALT, AST, ALP, or total bilirubin, a baseline diagnosis and/or the cause of any clinically meaningful elevation must be understood and recorded in the eCRF.

If subject has $>$ ULN ALT, AST, or ALP that does not meet the exclusion limit at the baseline referenced in [Table 5–1](#) for LTFU subjects and at the Screening Visit for directly enrolled subjects, repeat the tests, if possible, prior to dosing to ensure there is no further ongoing clinically relevant increase. In case of a clinically relevant increase, inclusion of the subject must be discussed with the Medical Monitor.

Tests that result in ALT, AST, or ALP up to 25% above the exclusion limit may be repeated once for confirmation. This includes re-screening.

30. Subject has chronic liver disease.

6.2.2 Exclusion criteria for LTFU subjects only

- 2a. Subject had hypersensitivity to BRV or excipients or comparative drugs as stated in this protocol during the course of the core study.
- 4a. Subject had poor compliance with the visit schedule or medication intake in the core study.
- 7a. Subject ≥ 6 years of age has a lifetime history of suicide attempt (including actual attempt, interrupted attempt, or aborted attempt), or has suicidal ideation in the past 6 months as indicated by a positive response ("Yes") to Question 5 of the Columbia-Suicide Severity Rating Scale (C-SSRS) at the EV. If a subject has active suicidal ideation without a specific plan as indicated by a positive response ("Yes") to Question 4 of Columbia-Suicide Severity Rating Scale (C-SSRS) at the EV, the subject should be referred immediately to a Mental Healthcare Professional and may be excluded from the study based upon the Investigator's judgment of benefit/risk of continuing the subject in the study/on study medication.

6.2.3 Exclusion criteria for directly enrolled subjects only

8. Subject has previously received BRV.
9. Subject had concomitant use of LEV at the ScrV. In addition, the use of LEV is prohibited for at least 4 weeks prior to the ScrV.
10. Subject has epilepsy secondary to a progressive cerebral disease or tumor, or any other progressively neurodegenerative disease. Stable arteriovenous malformations, meningiomas or other benign tumors may be acceptable according to Investigator's opinion.
11. Subject has a history of primary generalized epilepsy.
12. Subject has a history of status epilepticus in the month immediately prior to the ScrV or during the Up-Titration Period.
13. Subject has a history or presence of pseudoseizures.
14. Subject is suffering only from febrile seizures.
15. Subject is on felbamate with less than 18 months continuous exposure. Subject who has taken felbamate for a combined duration of treatment and wash out of <18 months before the ScrV.
16. Subjects treated with vigabatrin who have visual field defects.
17. Subject has an allergy to pyrrolidone derivatives or investigational product excipients or a history of multiple drug allergies.
18. Subject has any clinically significant acute or chronic illness as determined during the physical examination or from other information available to the Investigator (eg, bone marrow depression, chronic hepatic disease, severe renal impairment, psychiatric disorder).
19. Subject has an underlying disease or is receiving a treatment that may interfere with the absorption, distribution, metabolism, and elimination of the study drug.
20. Subject has any medical condition that might interfere with his/her study participation (eg, serious infection or scheduled elective surgery).
21. Subject has a terminal illness.
22. Subject has any clinically significant deviations from reference range values for laboratory parameters as determined by the Investigator.
23. Subject has a clinically relevant ECG abnormality according to the Investigator.
24. Subject had major surgery within 6 months prior to the ScrV.
25. Subject received any investigational drug or device within the 30 days prior to the ScrV. The use of AEDs marketed for adults but not approved for pediatric use is not considered to be "investigational" for the purposes of this study.
26. Investigators' and co-Investigators' children may not be included as subjects in the study.
28. Subject has a lifetime history of suicide attempt (including an actual attempt, interrupted attempt, or aborted attempt), or has suicidal ideation in the past 6 months as indicated by a

positive response (“Yes”) to either Question 4 or Question 5 of the C-SSRS-Baseline/Screening at the ScrV.

6.3 Withdrawal criteria

Subjects are free to withdraw from the study at any time, without prejudice to their continued care. Withdrawal criteria are provided as follows, with criteria for potential drug-induced liver injury provided in Section 6.3.1.

Subjects must be withdrawn from the study if any of the following events occurs:

1. Subject develops an illness that, in the opinion of the Investigator, would interfere with his/her continued participation or would potentially be detrimental to his/her physical/mental health.
4. Subject takes prohibited concomitant medications as defined in the protocol.
5. Subject/parent(s)/legal representative(s) withdraws his/her/their consent.
6. There is confirmation of a pregnancy during the study, as evidenced by a positive pregnancy test.
7. The Sponsor or a regulatory agency requests withdrawal of the subject.
- 8a. Subject has an episode of convulsive status epilepticus, a prolongation of seizure duration, a worsening of seizure frequency, or emergence of a new type, that is considered by the Investigator to require intervention.
12. Investigator decides that withdrawal from further participation would be in the subject’s best interest.
13. Subject is unwilling or unable to continue, or the parent/legal guardian is unwilling or unable to allow the subject to continue in this study.
14. If subject is ≥ 6 years of age, subject has active suicidal ideation with a specific plan as indicated by a positive response (“Yes”) to Question 5 of the “Since Last Visit” or “Already Enrolled Subjects” (as applicable) version of the C-SSRS. The subject should be referred immediately to a Mental Healthcare Professional and **must** be withdrawn from the study.

Subjects may be withdrawn from the study if any of the following events occurs:

15. If subject is ≥ 6 years of age, subject has active suicidal ideation without a specific plan as indicated by a positive response (“Yes”) to Question 4 of the “Since Last Visit” or “Already Enrolled Subjects” version of C-SSRS. The subject should be referred immediately to a Mental Healthcare Professional and *may* be withdrawn from the study based on the Investigator’s judgment of benefit/risk of continuing with the subject in the study/on study medication.

If a subject from N01266 enrolls in EP0065 and either withdraws consent solely due to route of BRV administration (iv) or if the subject requires more than 10 iv doses of BRV, the subject may be allowed to return to N01266 after discussion with and agreement from the Medical Monitor. If a subject from N01266 is advised to withdraw from N01266 after participation in EP0065, the subject will be required to return to the N01266 to complete the required EDV, DTV, and SV assessments.

Investigators should attempt to obtain information on subjects, in the case of withdrawal or discontinuation. In case of discontinuation, the Investigator will complete a full evaluation documented as an EDV. For subjects considered as lost to follow-up the Investigator should make an effort (at least 1 phone call and 1 written message to the subject/parent[s]/legal representative[s]), and document his/her effort (date and summary of the phone call and copy of the written message in the source documents) to complete the final evaluation. All results of these evaluations and observations, together with a narrative description of the reasons for removing or discontinuing the subject, must be recorded in the source documents. The main reason for terminating the study will be reported in the eCRF.

Subjects who are withdrawn from the study should have their BRV dose down titrated weekly as described in Section 7.2. Refer to [Table 5–2](#) for procedures to be performed at the time of withdrawal.

Investigators should contact the Medical Monitor whenever possible to discuss the withdrawal of a subject in advance.

6.3.1 Potential drug-induced liver injury investigational medicinal product discontinuation criteria

Subjects with potential drug-induced liver injury (PDILI) must be assessed to determine if the investigational medicinal product (IMP) must be discontinued. In addition, all concomitant medications and herbal supplements that are not medically necessary should also be discontinued.

The PDILI criteria below require immediate and permanent discontinuation of IMP:

- Subjects with either of the following:
 - ALT or AST ≥ 5 xULN
 - ALT or AST ≥ 3 xULN and coexisting total bilirubin ≥ 2 xULN

The PDILI criterion below requires immediate discontinuation of IMP:

- Subjects with ALT or AST ≥ 3 xULN who exhibit temporally associated symptoms of hepatitis or hypersensitivity. Hepatitis symptoms include fatigue, nausea, vomiting, right upper quadrant pain or tenderness. Hypersensitivity symptoms include fever (without clear alternative cause), rash, or eosinophilia (ie, $>5\%$).

The PDILI criterion below allows for subjects to continue on IMP at the discretion of the Investigator.

- Subjects with ALT or AST ≥ 3 xULN (and ≥ 2 x baseline) and <5 xULN, total bilirubin <2 xULN, and no eosinophilia (ie, $\leq 5\%$), with no fever, rash, or symptoms of hepatitis (eg, fatigue, nausea, vomiting, right upper quadrant pain or tenderness).

Evaluation of PDILI must be initiated as described in [Section 9.2.2](#). If subjects are unable to comply with the applicable monitoring schedule, IMP must be discontinued immediately.

Investigators should attempt to obtain information on subjects in the case of IMP discontinuation to complete the final evaluation. Subjects with PDILI should not be withdrawn from the study until investigation and monitoring are complete. All results of these evaluations and

observations, as well as the reason(s) for IMP discontinuation and subject withdrawal (if applicable), must be recorded in the source documents. The eCRF must document the primary reason for IMP discontinuation.

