9.2.2 Evaluation of PDILI

The PDILI IMP discontinuation criteria for this study are provided in [Section 6.3.1](#), with the accompanying required follow-up investigation and monitoring detailed below. All PDILI events must be reported as an AE and reported to the study site and Sponsor within 24 hours of learning of their occurrence. Any PDILI event that meets the criterion for potential Hy's Law must be reported as an AE of special interest (see [Section 9.1.1.3](#)), and, if applicable, also reported as an SAE (see [Section 9.1.2.3](#)).

Evaluation of PDILI consists of the diagnostic testing and continued monitoring included in [Table 9–2](#) (specific tests dependent on laboratory results and corresponding symptoms) and consultation with a local hepatologist (if applicable; discussed in [Section 9.2.2.1](#)). The local hepatologist is the expert usually consulted by the treating physician for assessment and management of potential hepatic disease. This would usually be a hepatologist, but may be a gastroenterologist. Additional investigation and monitoring may be required and adapted based on the diagnosis after the cause of the liver injury/abnormality is confirmed (details in [Section 9.2.2.4](#)).

The results of all monitoring, including laboratory testing and other testing, should be made available to the study site and Sponsor.

All initial tests resulting in abnormal hepatic laboratory values need to be repeated, but appropriate medical action must not be delayed waiting for the repeat result.

If tests are done locally for more rapid results, a concurrent sample should also be sent to the central laboratory whenever possible. Medical care decisions are to be made initially using the most rapidly available results and a conservative approach must be taken if the results from the 2 laboratory tests are significantly different. Data from the local and central laboratory are to be recorded on the applicable eCRF pages.

When IMP is discontinued, all concomitant medications and herbal supplements that are not medically necessary should also be discontinued. In these cases, the Investigator should also consider dose reduction for medically necessary concomitant medication and consider changing any medically required concomitant medication known to be hepatotoxic to a suitable alternative.

Rechallenge with a substance potentially causing drug-induced liver injury is dangerous, may be fatal, and must not occur.

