The table below summarizes the approach to investigate PDILI.

This document cannot be used to support any marketing authorization
application and any extensions or variations thereof.

PUBLIC COPY

Table 9–2: Required investigations and follow up for PDILI

Laboratory value		Symptoms ^a of hepatitis or hypersensitivity	Immediate		Follow up	
ALT or AST	Total bilirubin		Consultation requirements	Actions	Testing	Evaluation
≥3xULN	≥2xULN ^b	NA	Hepatology consult. ^c Medical Monitor must be notified within 24 hours (eg, by laboratory alert) and subject discussed with Medical Monitor ASAP.	Immediate, permanent IMP discontinuation.	Essential: Must have repeat liver chemistry values and additional testing completed ASAP (see Section 9.2.2.3); recommended to occur at the site with HCP.	Monitoring of liver chemistry values at least twice per week until values normalize, stabilize, or return to within baseline values. ^d
≥3xULN	NA	Yes		Immediate, temporary or permanent, IMP discontinuation.		
≥5xULN (and ≥2x baseline)	<2xULN	No	Discussion with Medical Monitor required. Hepatology consult required if ALT/AST ≥8x ULN.	Immediate, permanent IMP discontinuation.	Essential: Every attempt must be made to have repeat liver chemistry values and additional testing completed within 48 hours at the site with HCP (see Section 9.2.2.3).	

Table 9–2: Required investigations and follow up for PDILI

Laboratory value		Symptoms ^a of hepatitis or hypersensitivity	Immediate		Follow up	
ALT or AST	Total bilirubin		Consultation requirements	Actions	Testing	Evaluation

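### Table 9-2 lets a symptomatic child with ALT/AST ≥5xULN and bilirubin <2xULN be stopped only temporarily, where Section 6.3.1 demands a permanent stop

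*Protocol*

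**What the plan says.** Section 6.3.1 sets three tiers for potential drug-induced liver injury (PDILI).

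- **Permanent stop.** The lead-in is "The PDILI criteria below require immediate and permanent discontinuation of IMP". Two criteria follow. One is "ALT or AST ≥ 5 xULN", with nothing attached about symptoms, bilirubin or baseline. The other is ALT or AST ≥3xULN together with total bilirubin ≥2xULN.
- **Immediate stop, permanence not stated.** The lead-in is "The PDILI criterion below requires immediate discontinuation of IMP". It covers subjects with ALT or AST ≥3xULN "who exhibit temporally associated symptoms of hepatitis or hypersensitivity". No upper limit is given.
- **Continuation at the investigator's discretion.** This covers 3 to <5xULN (and at least twice baseline), bilirubin <2xULN, and no symptoms or eosinophilia.

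Table 9-2 in Section 9.2.2 turns these tiers into actions. Its symptomatic row reads ALT/AST ≥3xULN, bilirubin not applicable, symptoms yes, and the action is "Immediate, temporary or permanent, IMP discontinuation". Its next row, labelled "≥5xULN (and ≥2x baseline"), calls for a permanent stop but is limited to bilirubin <2xULN and symptoms no.

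Section 9.2.2 says "The PDILI IMP discontinuation criteria for this study are provided in" Section 6.3.1, and introduces the table with "The table below summarizes the approach to investigate PDILI". Section 9.2.2.2 refers the reader to both Section 6.3.1 and Table 9-2 for the immediate action.

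**The concern.** In Section 6.3.1 symptoms aggravate the picture: at 3 to <5xULN with bilirubin <2xULN they turn optional continuation into an immediate stop. At ≥5xULN with bilirubin <2xULN the table works the other way. A child without symptoms (and with values at least twice baseline) must stop permanently, while a child with symptoms may be stopped temporarily. Nothing in Section 6.3.1 supports that reversal.

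A site acting on a laboratory alert may well work from the action table. It could record the stop as temporary, and leave a restart open, in a symptomatic child for whom Section 6.3.1 allows no restart. Two sites could handle the same case differently and each cite the protocol. This is a stopping rule for liver injury in children, so its action table should not be looser than the rule it summarises.

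**Working it through.** No arithmetic applies. The check takes every combination of ALT/AST band and bilirubin band for a **symptomatic** subject and asks what each text requires.

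Rows of Table 9-2, numbered here for reference:

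- R1: ≥3xULN, bilirubin ≥2xULN, symptoms not applicable. Permanent stop.
- R2: ≥3xULN, bilirubin not applicable, symptoms yes. Temporary or permanent stop.
- R3: ≥5xULN (and ≥2x baseline), bilirubin <2xULN, symptoms no. Permanent stop.
- R4: 3 to <5xULN (and ≥2x baseline), bilirubin <2xULN, symptoms no. Immediate stop not required.

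R3 and R4 require the absence of symptoms, so only R1 and R2 can match a symptomatic subject.

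| Case | ALT/AST | Bilirubin | Section 6.3.1 | Matching rows | Result |
|---|---|---|---|---|---|
| i | 3 to <5xULN | <2xULN | Immediate stop | R2 | Consistent |
| ii | 3 to <5xULN | ≥2xULN | Permanent | R1 and R2 | R1 gives permanent; R2 overlaps |
| iii | ≥5xULN | <2xULN | Permanent | R2 only | **Conflict** |
| iv | ≥5xULN | ≥2xULN | Permanent | R1 and R2 | R1 gives permanent; R2 overlaps |

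Only in case iii does no matching row restrict the action to a permanent stop. In cases ii and iv, R1 supplies the permanent stop, although R2 also matches and is looser.

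For comparison, an asymptomatic subject with ≥5xULN (and ≥2x baseline) and bilirubin <2xULN falls in R3 and must stop permanently, as Section 6.3.1 requires. The mismatch is therefore confined to the symptomatic row.

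Repeating the check with R2 reworded to be permanent at ALT/AST ≥5xULN or bilirubin ≥2xULN, and otherwise temporary or permanent:

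- Case i is unchanged.
- Case iii becomes permanent.
- Cases ii and iv become permanent in both matching rows.

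All four cases then agree with Section 6.3.1.

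**The case against.** The best defence is that both texts can be obeyed at once. A permanent stop satisfies R2 as well as Section 6.3.1, and the wording of R2 can be read as spanning two tiers, with Section 6.3.1 deciding which applies. Section 9.2.2 names Section 6.3.1 as the home of the discontinuation criteria, and the table is presented as a summary of how to investigate. Safeguards also surround the affected child:

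- the stop is immediate under either text;
- Section 9.2.2 forbids rechallenge with a drug that may have caused liver injury;
- Section 9.2.2.1 requires the Medical Monitor to be notified within 24 hours and the case to be discussed as soon as possible.

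No endpoint, analysis set or estimate is affected, so the matter could be seen as a labelling slip in one cell.

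Much of this stands, and it is why the point is narrow. It does not remove the conflict. Section 9.2.2.2 makes the table operative for the stop decision, and nothing says that Section 6.3.1 prevails where the two differ. The rechallenge ban does not settle permanence either, because the same table expressly allows a temporary stop and so contemplates restarting in some PDILI cases. Section 6.3.1 offers no such route at ≥5xULN. That a careful reader would choose the stricter text does not justify printing a looser one.

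The objection is also right that adding the bilirubin condition to R2 is tidying, since R1 already covers those cases.

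**Conclusion.** The inconsistency is real and should be corrected. It lies in one action cell of Table 9-2 and affects symptomatic subjects with ALT/AST ≥5xULN and total bilirubin <2xULN. How many such subjects to expect cannot be derived from the protocol. The stopping rule in Section 6.3.1 is not itself in question; the table that puts it into practice is weaker than the rule for this group.

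The conclusion rests on two readings: that the ≥5xULN criterion in Section 6.3.1 applies regardless of symptoms, as its wording states, and that the symptom column of Table 9-2 restricts each row as printed. Practical risk is limited by the immediate stop, the rechallenge ban and Medical Monitor involvement.

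**What to change.** Replace the action in the symptomatic row of Table 9-2 with:

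> Immediate IMP discontinuation; permanent if ALT or AST ≥5xULN or total bilirubin ≥2xULN, otherwise temporary or permanent.

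Keep that row's consultation and testing requirements. No other row and no text in Section 6.3.1 needs to change for this point.

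The cost is the wording of one cell in an amendment, with whatever approvals Section 13.5 requires; it could go in with the next amendment. It adds no assessments, visits or data.
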